9.2.1.2 Handling of Specimens(s)

The fresh frozen or fixed tissue will be analyzed with protein based assay(s) and/or gene transcriptional assay(s) to evaluate drug induced changes in MAPK signaling. Abrogation of negative feedback pathways with small molecule targeted therapies leading to activation of alternate signaling pathways to mediate drug resistance have been well described. Candidate signaling pathways that may be activated in response to trametinib-mediated MEK inhibition will also be interrogated.

Profiling of cellular transcriptional output has been validated as a means of distinguishing tumor cell susceptibility to MEK inhibition (Dry et al., 2010) and the differential impact of MEK inhibition upon *BRAF* MUT versus WT tumors (Pratilas et al., 2009). In the thyroid, *DUSPs* are particularly useful markers of MAPK activity, and may be explored in the samples (Chakravarty et al., 2011). Additionally, the re-expression of some key thyroid-specific genes such as *NIS* will be evaluated (Chakravarty et al., 2011).

The approach(es) utilized will be determined by the availability of assay(s) and funding at the time of analysis. This analysis could also be performed on the submitted archival tissue in addition to, or in lieu of, analysis of tissues obtained from research biopsies.

9.3 Special Studies

Not Applicable

10. STUDY CALENDAR

Pre-Study and Weeks 1-5 study calendar for all patients:

NOTE FOR THE ^{124}I PET/CT LESIONAL DOSIMETRY: Changes in the scheduling of the tests and/or assessments below, including the first or second ^{124}I PET/CT lesional dosimetry process, may be considered in the event of holidays, scheduling conflicts, unanticipated delays (e.g. delays in ^{124}I shipment, weather, etc...) or interruptions in trametinib therapy after discussion with the Principal Investigator. (NOTE: Week and day number designations may change if there are interruptions in study treatments/assessments.)

	Pre-Study ^f	Wk 1						Wk 2	Wk 3	Wk 4	Wk 5				
		D1	D2	D3	D4	D5	D6 & D7				D1	D2	D3	D4	D5
Trametinib ^a							X	X	X	X	X	X	X	X	X
Adherence to low iodine diet ^b	X ^b	X	X	X	X	X			X ^b	X	X	X	X	X	
Thyrogen ^c		X	X							X	X				
^{124}I administration (approximately 6 mCi) ^d				X								X			
^{124}I PET/CT						X								X	
beta-HCG ^g	X ^g	X ^j								X ^j					
Tumor Genotyping	X ^e														
Informed consent	X														
Demographics	X														
Medical history	X														
Concurrent meds	X	X-----												X	
Physical exam	X					X ^k		X						X ^k	
Vital signs	X					X ^k		X						X ^k	
Height	X														
Weight	X					X ^k		X						X ^k	
Performance status	X					X ^k		X						X ^k	
CBC w/diff, plts	X	X ^k						X		X ^k					
chemistry ^h	X	X ^k						X		X ^k					
PT/aPTT (include INR)	X														
EKG	X														
Echocardiogram or MUGA ^m	X														
Ophthalmology exam ⁿ	X														
Adverse event evaluation		X-----												X	
Radiologic evaluation (CT(s) and/or MRI(s)) for tumor measurements NO IODINATED CONTRAST IS ALLOWED	X														
TSH, free T4, thyroglobulin, thyroglobulin antibody ^l		X	X	X	X	X		X	X	X	X	X	X	X	
Research blood sample ^o	X														
Research biopsy ⁱ	X							X							

a: Trametinib is to be started on Week 1, Day 6 at 2 mg orally daily. If the second lesional dosimetry with ^{124}I PET/CT indicates that RAI should be given, trametinib will be continued until 2 days after RAI has been administered. If the lesional dosimetry with ^{124}I PET/CT indicates that RAI should not be given, trametinib may or may not be discontinued (see the appropriate table below). Ideally, patients will remain on trametinib continuously for a minimum of 7 days prior to the performance of the PET/CT for the second lesional dosimetry (scheduled here in Week 5), (this is not a requirement). To achieve this, the second lesional dosimetry may be rescheduled at the discretion of the treating physician. If the second lesional dosimetry is delayed more than 4 weeks, the MSK Principal Investigator and the treating physician will determine if the patient should be continued or removed from the study. If trametinib is missed for ≥ 7 days total or interruptions in trametinib dosing have occurred prior to or during whole body and blood dosimetry and ^{131}I (RAI) treatment, then having some or all of the doses made up and rescheduling the study assessments/treatments may be considered after discussion with the Principal Investigator (this is not a requirement).

b: Patients should adhere to a low iodine diet for 5 days prior to the initiation of the lesional dosimetry process (considered in the first day of the 5 day process) until its completion (the fifth day when the PET/CT is performed). Patients who go on to whole body and blood dosimetry and ^{131}I treatment will be continued on the low iodine diet through 1 day after ^{131}I is given. Please see [Appendix B](#) for details of the low iodine diet.

- c: 0.9 mg Thyrogen will be administered intramuscularly on Days 1 and 2 of Weeks 1 and Week 5.
- d: Approximately 6 mCi (range 4-7 mCi) of ^{124}I administered orally.
- e: Tumor genotyping can be conducted on the primary tumor, recurrent tumor, or a metastasis. Results can be obtained any time before patient is registered to the study.
- f: All Pre-Study evaluations must be done ≤ 28 days prior to Week 1 Day 1 unless otherwise specified.
- g: pregnancy test (for women of childbearing potential). Pre-study beta-HCG levels need to be drawn within 2 weeks prior study registration.
- h: chemistry includes albumin, alkaline phosphatase, total bilirubin, bicarbonate, BUN, calcium, chloride, creatinine, glucose, phosphorus, potassium, total protein, SGOT [AST], SGPT [ALT], sodium.
- i: The first research biopsy will be performed prior to initiation of Week 1 Day 1. The second biopsy will be performed in Week 3 of the study. It is preferred, but not required, that the second biopsy be performed upon the same tumor that was sampled with the first research biopsy, if safe and feasible. Patients may be exempt from biopsy if either the investigator or person performing the biopsy judges that no tumor is accessible for biopsy or that biopsy poses too great of a risk to the patient (if the only tumor accessible for biopsy is also the only lesion that can be used for RECIST v1.1 response evaluation, then the patient may be exempt from biopsy after discussion with the MSK Principal Investigator). Radiologic guidance (CT, MRI or ultrasound guided) approaches and obtaining multiple cores to ensure sufficient biopsy material (at least 3 cores preferred) are allowed as long as it is considered reasonably safe for the patient.
- j: beta-hcg (for women of childbearing potential) must be done within 2 days prior to administering ^{124}I .
- k: The days designated for these evaluations/tests are only suggestions. These can be scheduled for any time during the week for which they are scheduled.
- l: TSH, free T4, thyroglobulin, and thyroglobulin antibody will be drawn on Day 1 of weeks 1 and 5 (preferably prior to administration of Thyrogen on that day). Only TSH will be drawn on Day 3 during Weeks 1 and 5. TSH and Thyroglobulin total and antibody will be drawn on Days 5 of Weeks 1 and 5 (i.e., the weeks that the ^{124}I PET/CT are to be performed). TSH and Free T4 will be drawn for the Week 3 assessment (thyroglobulin and thyroglobulin antibodies are not required to be drawn during this week).
- m: The same modality (echocardiogram or MUGA) should be used at baseline and at follow-up.
- n: Ophthalmology exams should be obtained at baseline, and if clinically indicated, during study. Ophthalmology exam should include Ocular Coherence Tomography, fundoscopy, tonometry, visual field examination, and corrected visual acuity assessments.
- o: For the research blood specimen, approximately 10 mL of blood will be collected in a tube with EDTA (usually lavender top) any time after the informed consent has been signed.

Study Calendar for PATIENTS WHO RECEIVE RAI (Week 5, Day 6 and beyond)

If the second lesional dosimetry with trametinib reveals sufficient tumoral iodine incorporation to deliver a dose of $\geq 2,000$ cGy with ≤ 300 mCi of RAI, then the patient will continue on trametinib and a low iodine diet (as decided by the treating physician(s)). The schedule of treatments and assessments for these patients are detailed below (NOTE: Week and day number designations may change if there are interruptions in study treatments/assessments):

	Wk 5	Wks 6 & 7 D6 & D7	5 weeks (+/- 2 weeks) after RAI therapy	About 3 or 4 months after RAI	About 6 months after RAI (+/- 1 week)
Trametinib ^a	X	X			
Adherence to low iodine diet ^a	X	X			
Whole body and blood dosimetry and ^{131}I (RAI) treatment with Thyrogen stimulation (per standard of care) ^a		X			
Concurrent meds	X-----X				
Physical exam			X		
Vital signs			X		
Weight			X		
Performance status			X		
CBC w/diff, plts			X		
chemistry ^b			X		
TSH, free T4, thyroglobulin, thyroglobulin antibody			X	X	X
beta-HCG		X ^c			
Echocardiogram or MUGA ^c			X ^c		
Adverse event evaluation	X-----X (Monitored for 30 days following the last dose of trametinib.)				
Radiologic evaluation (CT(s) and/or MRI(s)) for tumor measurements NO IODINATED CONTRAST IS ALLOWED	X ^d			X ^d	X ^d

a: Patients will be continued on trametinib and a low iodine diet. Whole body and blood dosimetry and thyrogen-stimulated ^{131}I (RAI) treatment is to be completed no later than in Week 7 (unless changes/interruptions of study drug administration and/or study assessments had to be enacted such that whole body and blood dosimetry and therapeutic RAI has to be completed after Week 7)(this dosimetry will be conducted as per institutional guidelines). Trametinib will be continued through 2 days after therapeutic ^{131}I administration. The low iodine diet will be continued through 1 day after ^{131}I treatment. ^{131}I therapeutic dosing will be guided by the dosimetric determination of the maximum tolerated activity (MTA): the ^{131}I activity administered concomitantly with trametinib is not to exceed the MTA plus 3 mCi (i.e., $[\text{MTA}] \leq [\text{MTA} + 3 \text{ mCi}]$). **Delays in performing the whole body and blood dosimetry and RAI treatment due to holidays, scheduling conflicts, or interruptions in trametinib therapy may be allowed after discussion with the MSK Principal Investigator.**

b: chemistry includes albumin, alkaline phosphatase, total bilirubin, bicarbonate, BUN, calcium, chloride, creatinine, glucose, phosphorus, potassium, total protein, SGOT [AST], SGPT [ALT], sodium.

c: beta-hcg (for women of childbearing potential). To be completed within 2 days prior to administration of RAI.

d: CT(s) WITHOUT CONTRAST and/or MRI(s) to reassess disease is/are to be done after completion of the second ^{124}I PET/CT scan and before the administration of RAI. Scans will be repeated about 3 to 4 months after RAI and about 6 months (+/- 1 week) after RAI; it is requested that attempts be made to have scans performed as close to 6 months from the time RAI (^{131}I) was administered if possible to best assess the 6-month PFS endpoint. If an additional scan is required to confirm a complete or partial response after the 6 month scan, an additional radiologic evaluation should be completed within 1 to 3 months after the last scan. Schedule of the radiographic assessments may be altered if there are disruptions of the planned assessment/treatment schedule after discussion with the Principal Investigator. Failure to complete the scans after RAI will not be considered protocol violations with the exception of those scheduled for 6 months following RAI.

e: Followup echocardiogram or MUGA should be performed within 1 month after discontinuing trametinib. The same modality used at baseline should be performed for this followup.

Study Calendar for PATIENTS WHO DO NOT RECEIVE RAI (Week 5, Day 6 and beyond)

For both COHORT A (RAS MUT) and B (BRAF/RAS WT) patients: If analysis of the second lesional dosimetry suggests that therapeutic RAI will not be given, it will be concluded that the patient's cancer is still refractory to RAI and RAI will not be administered. Such patients may be continued on trametinib alone (in Cohort C) if 1) the treating physician determines it to be clinically reasonable, and 2) the patient agrees to continue on trametinib. **If these conditions are not met, then trametinib will be discontinued and the patient removed from the study; for these patients, the "Off Study" requirements detailed in the table below will be performed within 30 days of trametinib discontinuation.**

(NOTE: After completion of the designated evaluations/treatments through Week 5 detailed in the "*Pre-Study and Weeks 1-5 study calendar for all patients*" above, the subsequent week will be considered Cycle 2, Week 1 of treatment (what would have been considered Week 6 in the study calendars above). Week and day number designations may change if there are interruptions in study treatments/assessments:

	Cycle 2 Wk 1	Cycle 2 Wk 2	Cycle 2 Wk 3	Cycle 2 Wk 4	Cycle 3+ Wk 1	Off Study ^c
Trametinib	X	X	X	X	X	
Concurrent meds	X-----				X	
Physical exam			X		X ^b	X
Vital signs			X		X ^b	X
Weight			X		X ^b	X
Performance status			X		X ^b	X
CBC w/diff, plts			X		X ^b	X
chemistry ^a			X		X ^b	X
TSH, free T4, thyroglobulin, thyroglobulin antibody					X (to be checked about every 2 cycles) ^b	
Echocardiogram or MUGA	Approximately every 3 cycles starting with Cycle 4. Use the same methodology for baseline and follow up.					
Adverse event evaluation	X-----				X	X
Tumor measurements	CT and/or MRI will be performed every 8 weeks (+/- 1 week) (or approximately every 2 cycles) with the first scan assessment on trametinib treatment to be performed during Cycle 2, Week 4 or Cycle 3, Week 1. After 10 months on treatment with trametinib, scans will be performed every 12 weeks (+/- 1 week)(or approximately every 3 cycles). If early, unplanned CT and/or MRI scan(s) is/are performed which can serve as an assessment of response prior to the protocol-mandated radiologic scans, the next set of protocol-mandated scans may be rescheduled to occur in 8 weeks (+/- 1 week) or 12 weeks (+/- 1 weeks) (according to the criteria described above) from the time of the last assessment (this is not mandatory). Documentation (radiologic) must be provided for patients removed from study for progressive disease. Objective responses should be confirmed with a second assessment performed at least 4 weeks later.					

a: chemistry includes albumin, alkaline phosphatase, total bilirubin, bicarbonate, BUN, calcium, chloride, creatinine, glucose, phosphorus, potassium, total protein, SGOT [AST], SGPT [ALT], sodium.
 
b: After the completion of Cycle 2, these tests and evaluations will be done once each cycle, preferably on week 1 of each cycle if possible. The exceptions are blood tests for TSH, free T4, thyroglobulin, and thyroglobulin antibody which are to be checked every 8 weeks +/- 1 week (about every 2 cycles).
 
c: These off study assessment will be performed within 30 days of discontinuing trametinib.
						

Trametinib toxicities will be monitored only for 30 days following the last dose of trametinib.

The impact of more than one month of trametinib therapy upon RAI uptake and/or efficacy is unknown. Patients who do not receive ^{131}I therapy after the second ^{124}I PET/CT scan and remain on trametinib may be evaluated with a third Thyrogen-stimulated ^{124}I PET/CT scan (with the procedure detailed in Section 10.0 for Week 5) 4 weeks or more after completion of the prior ^{124}I PET/CT scan process. If the lesional dosimetry criteria for ^{131}I therapy is met on the third ^{124}I PET/CT, patients can go on to be prepared for/treated with ^{131}I and followed as detailed in Section 10.0 (in the calendar under the heading “*Study Calendar for PATIENTS WHO RECEIVE RAI (Week 5, Day 6 and beyond)*” (treatment with ^{131}I is not mandatory). If the third ^{124}I PET/CT scan results do not fulfill the ^{131}I treatment criteria, patients may continue on trametinib alone with the evaluations/treatments required for Cohort C.

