5.3 Duration of Therapy

In the absence of treatment delays due to adverse event(s), treatment may continue until one of the following criteria applies:

1. Disease progression (however, Cohort A and B patients with evidence of clinical disease progression or RECIST v1.1 radiographic progression (such as on the ^{124}I PET/CTs or other scans) prior to the 6-month evaluation of the primary/secondary endpoints may be continued on treatment and the study if the treating physician deems it clinically reasonable),
2. Intercurrent illness that prevents further administration of treatment,
3. Unacceptable adverse event(s),
4. Patient decides to withdraw from the study,
5. General or specific changes in the patient's condition render the patient unacceptable for further treatment in the judgment of the investigator,
6. (For Cohort A and B patients) It is determined that a patient will not receive therapeutic ^{131}I and the treating physician determines that it is not clinically reasonable to continue with trametinib therapy alone or the patient does not want to continue with trametinib therapy alone,
7. For patients who do receive therapeutic ^{131}I , trametinib will be continued until 2 days after ^{131}I is administered. Patients will remain on study for tumor assessments that will be completed approximately 6 months after ^{131}I therapy. Safety monitoring for trametinib related toxicities will be continued until 30 days after last trametinib dose.
8. All study therapy has been completed as planned.

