5.4 Duration of Follow Up

Adverse events will be followed for 30 days after the last dose of trametinib. Patients removed from study for unacceptable adverse event(s) will be followed until resolution or stabilization of the adverse event.

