7.1.3 Adverse Event List for ^{131}I

Early side effects (may develop immediately or during the first days after RAI treatment): In 10-20% patients, painful swelling of the remnant thyroid tissue or metastases occur. Nausea or vomiting may occur due to radiation induced gastritis. In some patients salivary complications like salivary gland pain, swelling, altered taste, epiphora, change in the taste or smell occurs. In two-thirds of patients, transient and non-clinically significant decrease in thrombocytes and leukocytes may develop.

Late side effects (may develop weeks, months or even years after radioiodine therapy): The most frequent late side effect is related to decreased salivary gland function. In approximately 5%, thrombocytopenia and leukopenia may develop. In approximately 1-2% of patients, leukemia or bone marrow aplasia may occur especially with cumulative doses of ^{131}I . Pulmonary fibrosis can develop in patients with iodine avid lung metastases in whom a delivered activity exceed the maximum tolerable activity determined by dosimetry. The females of childbearing age should avoid pregnancy for 6-12 months after RAI therapy. In males, transient elevation of follicle stimulated hormone (FSH) following ^{131}I therapy may occur. In very rare case, persistent gonadal dysfunction i.e azoospermia may occur.

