7.4 Routine Adverse Event Reporting

All Adverse Events **must** be reported in routine study data submissions. **AEs reported through CTEP-AERS must also be reported in routine study data submissions.**

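### In RAI-treated patients the written adverse event window closes about day 32 after RAI, before the day-35 safety visit, so counting a non-serious finding can depend on visit date and on which section is followed

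*Combined protocol and SAP*

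**What the plan says.** **Last dose.** Note a to the RAI calendar (Section 10) states: "Trametinib will be continued through 2 days after therapeutic" radioiodine.

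**End of adverse event follow-up.** Two places set the limit for adverse events generally:
- The adverse event row of the RAI calendar: "Monitored for 30 days following the last dose of trametinib".
- Section 5.4: "Adverse events will be followed for 30 days after the last dose of trametinib".

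Two places set it for a narrower class:
- Section 5.3, item 7, written for RAI-treated patients: "Safety monitoring for trametinib related toxicities will be continued until 30 days after last trametinib dose".
- Section 13.4 repeats the 30-day limit for trametinib-related toxicity. It also counts every patient as evaluable for toxicity from the first dose, with no end date.

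**No end date.** Section 7.4 requires that all adverse events "be reported in routine study data submissions" and gives no closing date.

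**The safety visit.** After RAI, physical examination, vital signs, weight, performance status, CBC and chemistry are marked only in the column headed "5 weeks (+/- 2 weeks) after RAI therapy". The columns at 3 to 4 months and at 6 months hold thyroid tests and scans.

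**Contrast.** For patients who do not receive RAI, note c of their calendar says: "These off study assessment will be performed within 30 days of discontinuing trametinib".

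**The concern.** A visit held exactly on schedule falls after the written end of adverse event follow-up, and it is the only planned look at blood counts, chemistry and examination after RAI. Two patients with the same mild cytopenia, one seen on day 30 and one on day 35, both comply with the calendar, yet only the first is inside the window of Section 5.4.

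The stake is the safety summary. Section 13.4 makes the safety of trametinib in combination with RAI a secondary endpoint in Cohorts A and B, with toxicities reported individually and summarized. Section 7.1.3 lists thrombocytopenia and leukopenia among late RAI effects, which it says may appear weeks to years after treatment. A toxicity table should not turn on the appointment date or on which section the person coding the data happens to follow.

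**Working it through.** The plan states no day number after RAI, so there is no figure to reproduce. The check is calendar arithmetic with RAI as day 0.

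**Inputs**
- Last trametinib dose: day 2 (RAI calendar, note a).
- Follow-up after last dose: 30 days (RAI calendar; Section 5.4).
- Safety visit: 5 weeks ± 2 weeks after RAI (RAI calendar, column heading).

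**Steps**
1. Window closes: 2 + 30 = day 32.
2. Visit: nominal 5 × 7 = day 35; allowed 35 − 14 = day 21 to 35 + 14 = day 49; 49 − 21 + 1 = 29 allowed days.
3. Inside the window: days 21 to 32 = 12 days (12/29 = 41%). After it: days 33 to 49 = 17 days (17/29 = 59%).
4. Nominal visit: 35 − 32 = 3 days after closing (35 − 2 = 33 days after the last dose). Latest allowed visit: 49 − 32 = 17 days after closing (49 − 2 = 47 days after the last dose).

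**Sensitivity to the last-dose day**

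| Last dose (day after RAI) | Window closes | Allowed days after closing |
|---|---|---|
| 0 | day 30 | 19/29 (66%) |
| 1 | day 31 | 18/29 (62%) |
| 2 (as written) | day 32 | 17/29 (59%) |
| 3 | day 33 | 16/29 (55%) |

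The nominal day-35 visit is outside in every row.

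**How each section treats a non-serious finding first seen on day 35**

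| Place | Judged trametinib-related | Judged RAI-related only |
|---|---|---|
| RAI calendar; Section 5.4 | outside | outside |
| Section 5.3 item 7; Section 13.4 monitoring sentence | outside | not addressed |
| Section 13.4 evaluability sentence; Section 7.4 | no end date | no end date |

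A trametinib-related finding is outside every window that is written down. For an RAI-related finding the sections give different answers.

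**The case against.** The strongest reply is that Section 13.4, which governs the analysis, restricts only trametinib-related toxicity and sets no end for other toxicity, and that Section 7.4 requires all adverse events to be reported. On that reading a day-35 RAI cytopenia is counted. This stands as a possible reading. It does not settle the matter, because Section 5.4 and the calendar apply the limit without regard to attribution, and those are what sites follow when they collect data.

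Other points narrow the concern and are accepted:
- Section 7.3.2, footnote 1, keeps serious events with possible, probable or definite attribution reportable beyond 30 days. Section 7.5 requires secondary malignancies to be reported with no stated time limit. Section 5.4 follows patients removed for unacceptable events until resolution or stabilization.
- A symptom that began by day 32 can be counted by its onset date even if reported later. The gap mainly concerns laboratory and examination findings with no earlier date.
- Note e puts the ECHO/MUGA, which sits in the same column, within 1 month of stopping trametinib, about day 32. A site that does the column's assessments together would tend to visit earlier.
- The drawn end of the adverse event row cannot be placed in the extracted table. If it reaches the 5-week column, an evaluation is scheduled there, but the written 30-day note still applies.

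Three stronger readings are tempting, and the documents do not support them. A reader might infer that 59% of RAI-treated patients will be seen too late; that figure is a share of allowed days, and the plan gives no distribution of visit dates. A reader might infer that post-RAI toxicity goes unobserved; the tests are still drawn at the visit, and only their place in the summary is uncertain. A reader might apply the roughly 5% late-cytopenia rate in Section 7.1.3 to obtain a number of lost cases; that rate covers effects arising over weeks to years, not those first seen on days 33 to 49.

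**Conclusion.** The concern holds in limited form. The written limit in Section 5.4 and the RAI calendar ends follow-up 3 days before the nominal safety visit and up to 17 days before the latest allowed one, and Sections 5.3 and 13.4 word the limit differently. Depending on scheduling, this could touch none or all of the RAI-treated patients, a subset of the 35 planned (25 in Cohort A, 10 in Cohort B); no case count can be given. It affects only non-serious findings first detected after about day 32, in a descriptive secondary summary. Primary endpoints, error rates and sample size are untouched.

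The conclusion assumes that trametinib stops on day 2 after RAI, that the visit keeps to its stated window, and that the bracketed calendar note means what it says. Severity is low: a cheap improvement to the wording.

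**What to change.** In Sections 5.3, 5.4 and 13.4 and in the RAI calendar, state that adverse events of any attribution are collected in all RAI-treated patients through day 49 after RAI (47 days after the last trametinib dose when that dose is on day 2), and that the Section 13.4 combination safety summary uses this window. Day 49 covers all 29 allowed visit days.

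A fixed day is better than the later of 30 days after the last dose and the visit itself. Under that alternative a patient seen on day 21 would be followed to day 32 and one seen on day 49 to day 49, so observation time would still depend on scheduling.

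The cost is amendment wording and up to 49 − 32 = 17 more days of adverse event collection per RAI-treated patient. No visit or test is added. The change does not aim to capture RAI effects that arise months or years later.
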